### **16.3.1 Analysis of primary endpoints**

#### **16.3.1.1 Group 1 “RISK” patients:**

The Fisher’s exact test will be used to compare the proportion of non-responders in risk organs and the proportion of responders at week 6 and week 12.

#### **16.3.1.2 Group 2 “LOW RISK” patients:**

Reactivation (=progression in any organs) and death will be considered as events for the calculation of Reactivation Free Survival. The interval will start 6 months after therapy start, i.e. the time point when half of the patients are intended stop the continuation therapy (Arm LR6) whereas patients from the other randomized arm (Arm LR12) will further receive 6 months of continuation therapy. This means, randomized patients with reactivations within the first 6 months after randomization will not be included in the analyses. For censored patients the interval will be calculated until the date of the last response evaluation.

The proportion of reactivation free survival will be estimated according to the method of Kaplan-Meier and confidence intervals according to Dorey and Korn will be given for the reactivation free survival rate after 2 and 3 years. The primary statistical evaluation of the treatment effect will be done by log rank-test.

As a secondary aim the question whether a prolonged therapy can slow down the speed of reactivation will be considered. Retrospective data from LCH-I and LCH-II and the DAL-studies indicate that the hazards between 6 and 12 months of continuation therapy are proportional and constant in time (i.e. exponentially distributed reactivation free survival times). Therefore, a Weibull accelerated failure time model will be fitted to evaluate an acceleration factor. Moreover, a time dependent Cox regression model will be performed.

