### **9.2.1.3 Continuation treatment**

The overall therapy duration is 6 months for Arm LR 6 or 12 months for Arm LR 12 .

Pulses of oral prednisone PDN 40mg/m^2 in 3 doses, day 1-5 q 3 weeks, starting at day 1 of week 7 in patients NAD after course 1 or at day 1 of week 13 in patients NAD or AD better after course 2 until the end of month 6 or 12 from therapy start.

Vinblastine (VBL) 6mg/m^2 i.v. bolus, day 1 q 3 weeks, starting at day 1 of week 7 in patients NAD after course 1 or at day 1 of week 13 in patients NAD or AD better after course 2 until the end of month 6 or 12 from therapy start.

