### 16.1.2 Group 2 “LOW RISK” patients:

The Group 2-Study of LCH-III is a randomized controlled clinical trial for patients with multi-system LCH WITHOUT involvement of “RISK” organs (hematopoetic system, liver, spleen or lungs) and initial response at week 6 (NAD/AD better).

The random assignment to the treatment arms will be done in blocks stratified according to age at diagnosis ( $\leq 2$  years,  $> 2$  years) and local subcenters to ensure a balance within age groups, the local subcenters and within each pre-specified number of treatment assignments (=block). The randomization will be done in the local subcenter without delay after the first response evaluation 6 weeks after therapy start. Only patients with therapy response, i.e. regression (AD better) or resolution (NAD) after 6 weeks of initial treatment, will be eligible for randomization.

In addition, the impact of a prolonged initial treatment (= course2) for those patients who are not eligible for randomization is examined and compared with the historical control group of LCH-II patients.

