#### **16.2.1.2 Group 2 “LOW RISK” patients:**

The primary aim of the study is to compare the reactivation free survival rate in initial responders at week 6 with continuation treatment for 6 months (Arm LR 6) versus 12 months (Arm LR 12) in those patients without disease reactivation within the first 6 months.

If the null hypothesis is true, the reactivation rate of both randomized arms are equal. If the alternative hypothesis is true, there is a difference between the two arms in terms of reactivation frequency.

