## **16.3 ANALYSES**

The analyses of the primary and secondary endpoints will be done according to the intention-to-treat principle, i.e. the patients will be analyzed in their allocated treatment group, even in case of non-compliance or protocol violations.

The statistical analyses of the primary endpoint will be done with a two-sided significance level of 5 %. The statistical analyses of the secondary endpoints are exploratory. A separate analyses will be performed for each group (“RISK” and “LOW RISK”). In addition to the intention-to-treat analyses a secondary per protocol analyses will be done including all patients who were treated according to the originally assigned treatment arm without protocol violations (= unjustified dose modification, therapy delay and/or improper switch to another therapy within the first 12 months).

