### **16.5.2 Group 2 “LOW RISK” patients:**

Data from the previous LCH-II study indicate that the reactivation free survival rate of the control group (LR 6) is approximately exponential distributed with a 1-year reactivation free survival rate of about 65%. With this study we aim to show a 20% difference in the 1-year reactivation free survival rate (i.e. a 1-year reactivation free survival rate of 85% in patients with 12 month continuation treatment) with sufficient power.

To show a 20% difference at the 5% significance level with a power of 80% we would need a total of 36 events following the group sequential design (Jennison Turnbull).

85% of the patients with multi-system LCH without involvement of risk organs had an initial response. That means that with the expected annual recruitment of 40 multi-

[figure not shown]
system patients without risk organ involvement we can expect 34 patients per year who will be eligible for randomization. We expect that 85% of these patients will be randomized this means there will be 29 randomizations/year. About 5% of these patients will show a reactivation within 24 weeks of treatment, another 10% will possibly be lost to follow up within the first 24 weeks. Thus we will be able to recruit about 24 patients/year who will enter the analyses.

We considered a cautious estimated lost to follow up-rate in the calculation, which is assumed to be exponentially distributed with  $\lambda=0.664$ , i.e. about half of the patients are followed for more than one year. Given this lost to follow up rate and a minimum follow up of 2 years (period from entry of the last patients to the final analysis) following the group sequential design, we will need a recruitment period of about 6 years and a maximum sample size of 148 patients.

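### The Group 2 primary analysis has two time origins: its clock starts 6 months after therapy start, but it excludes reactivations up to 6 months after randomisation, about 6 weeks later

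*Protocol*

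**What the plan says.** Section 16.3.1.2 defines the primary interval for Group 2: "The interval will start 6 months after therapy start". It explains this as the point at which the LR 6 half is due to stop while LR 12 continues. Reactivation and death both count as events. The next sentence, offered as a consequence, sets the exclusion: "This means, randomized patients with reactivations within the first 6 months after randomization will not be included in the analyses".

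Other sections fix the dates around it:

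- Section 16.1.2 places randomisation "without delay after the first response evaluation 6 weeks after therapy start".
- Section 9.2.1.3 gives continuation treatment "until the end of month 6 or 12 from therapy start".
- Section 16.2.1.2 makes the primary comparison "in those patients without disease reactivation within the first 6 months", without saying from when the 6 months run.
- Section 16.5.2 sizes the exclusion: "About 5% of these patients will show a reactivation within 24 weeks of treatment".
- Section 16.3 says of the primary and secondary analyses that "the patients will be analyzed in their allocated treatment group, even in case of non-compliance or protocol violations".

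**The concern.** The clock and the exclusion are meant to share one date and do not. Up to month 6 of therapy the two arms are assigned the same treatment, so removing earlier reactivations is not tied to a treatment difference. In the following 6 weeks LR 6 is off treatment and LR 12 is on it. This is the first period in which the randomised question is tested, and the sentence as written deletes the reactivations that fall in it.

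Three things follow if a programmer applies the text literally:

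- Patients leave the primary analysis because of the primary outcome, after the arms have diverged.
- Those who stay contribute 6 weeks in which they cannot reactivate. Both Kaplan-Meier curves are then too high, and the Weibull model, which 16.3.1.2 justifies by constant hazards, is fitted to data with an artificial gap at the start.
- Reactivations are dropped but deaths in the same weeks are kept, although both are events.

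Section 13 schedules 6-weekly clinical examinations in the first year after therapy. The first LR 6 visit off treatment therefore falls about where the exclusion ends, and whether its findings count depends on which origin is used.

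**Working it through.** **Timeline.** Randomisation is at week 6, and 6 weeks is 42/30.4 = 1.4 months. Six months after randomisation is thus about 7.4 months after therapy start. The clock starts at 6.0 months, so the overlap is 6 weeks, d = 6/52.18 = 0.115 year.

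**Inputs (section 16.5.2 unless stated).** 1-year RFS 65% (LR 6) and 85% (LR 12), with exponential times assumed in both arms; 36 events; 148 patients, 74 per arm; recruitment about 6 years; minimum follow-up 2 years; loss to follow-up rate γ = 0.664 per year; 80% power; two-sided 5% (section 16.3).

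**The plan's own figure.**
- Hazards: −ln 0.65 = 0.431 and −ln 0.85 = 0.163 per year. Hazard ratio = 0.163/0.431 = 0.377 (unrounded hazards).
- Schoenfeld events, fixed design: 4 × (1.960 + 0.842)² / (ln 0.377)² = 33.0.
- The stated 36 implies a sequential inflation of 36/33.0 = 1.09. The protocol's Group 1 inflation, 228/202 = 1.129, would give 37.3. The 36 events are reproduced closely enough and are not in question.

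**Patients removed by the 6 weeks, ignoring loss to follow-up.**
- LR 6: 1 − exp(−0.431 × 0.115) = 4.8%.
- LR 12: 1 − exp(−0.163 × 0.115) = 1.9%.
- For LR 6 this is 4.8/35 = 14% of its first-year events.

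All RFS events in the window are taken as reactivations. Section 2 reports no deaths in the LCH II low-risk group.

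**Events expected with one origin.** Per arm: 74 × λ/(λ+γ) × the average of [1 − exp(−(λ+γ)T)] for T uniform from 2 to 8 years.
- LR 6: 74 × 0.387 = 28.6.
- LR 12: 74 × 0.189 = 14.0.
- Total 42.6.

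**Events lost as written.** Per arm: 74 × λ/(λ+γ) × [1 − exp(−(λ+γ)d)].
- LR 6: 3.4. LR 12: 1.3. Total 4.8 before rounding the parts.
- Share: 4.8/42.6 = 11%. Remaining: 37.9.

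**Apparent RFS.** Retained patients are at risk only from d onwards, so RFS at t years is exp(−λ(t − d)).

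| Years from clock start | Planned | As written | Difference |
|---|---|---|---|
| 1 | 65.0% v 85.0% | 68.3% v 86.6% | 20.0 → 18.3 points |
| 2 | 42.3% v 72.3% | 44.4% v 73.6% | 30.0 → 29.2 points |
| 3 | 27.5% v 61.4% | 28.9% v 62.6% | 34.0 → 33.7 points |

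**Power.** A log-rank simulation of 6,000 trials (single look at |Z| > 1.96, interim looks ignored) gives about 0.87 with one origin and 0.83 as written.

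**If reactivations cluster after stopping.** This is an assumption, as the protocol gives no such figure. With the LR 6 hazard in the first 6 weeks doubled or tripled, power is about 0.93 or 0.97 with one origin, and about 0.81 as written in both cases.

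**The case against.** The strongest reply is that this is a slip of one phrase. The sentence presents itself as a restatement of the month-6 start just defined, and section 16.5.2 counts the excluded reactivations in weeks of treatment. That is probably right. It does not remove the problem, because this sentence defines the primary analysis set and its literal meaning differs from the clock.

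A second reply is that the damage is small. About 38 events remain, above the target of 36, and power stays above 80% even under the clustering assumptions. At 2 and 3 years, where 16.3.1.2 places its confidence intervals, the difference between arms barely moves. This stands and limits the size of the point.

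A third reply concerns bias. A patient who reactivates in the first 6 weeks has left the risk set afterwards in any case, so later log-rank risk sets are the same with or without the exclusion. Under the constant hazards that 16.3.1.2 and 16.5.2 assume, the hazard ratio is unaffected. This also stands.

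One reading would align the dates differently. Sections 6.2.1 and 16.2.1.2 speak of 6 versus 12 months of continuation treatment. Counted from week 7, LR 6 would end about 6 months after randomisation. Sections 9.2, 9.2.1.3 and 16.3.1.2 count from therapy start instead, so the wording should be reconciled.

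**Conclusion.** The exclusion rule is wrong as written and should be corrected before analysis. Under the protocol's exponential rates and loss rate it costs about 5 of roughly 43 expected events, overstates 1-year RFS by about 3 points in LR 6 and 2 in LR 12, and lowers fixed-design power from about 0.87 to 0.83. A bias of the hazard ratio towards no difference would arise only if LR 6 reactivations cluster soon after stopping, which the documents do not state.

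A reader might infer more, but the documents do not support it:

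- **That the whole analysis contradicts intention to treat.** The month-6 restriction is declared in 16.2.1.2 and covers a period of identical assigned treatment, and 16.3 explains intention to treat only as analysis in the allocated arm. The sharp conflict is confined to the extra 6 weeks, although 16.3 should name the landmark.
- **That 24 weeks is a third window.** The protocol treats 24 weeks and 6 months as the same: section 2 uses both for the LCH II treatment duration, and the table in 10.3.2 passes from week 23 to month 6.
- **That 15% of randomised patients are lost to this rule.** The 15% in 16.5.2 is 10% expected loss to follow-up plus 5% reactivating within 24 weeks. Neither measures the disputed 6 weeks.
- **That randomisation should move to month 6.** That would be a redesign. Eligibility rests on response at week 6, and by month 6 patients rated intermediate or worse follow other paths in 10.3.2.

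**What to change.** - In 16.3.1.2, count the exclusion from therapy start instead of from randomisation, so that it ends where the clock begins.
- In 16.2.1.2, state the same origin for the 6 months.
- In 16.3, say that the Group 2 primary analysis is a month-6 landmark analysis by allocated arm, and add a supportive analysis of all randomised patients from randomisation.

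The cost is a few phrases and one extra analysis of data already collected. It needs no added patients or visits and no change to the time of randomisation. The choice should be documented before the arms are compared, because treatment is known to the centres and an origin chosen after seeing the data would not be credible.

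### Group 2 primary analysis: the interval opens 6 months after therapy start, but the exclusion of early reactivations runs to 6 months after randomisation, about 6 weeks later

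*Protocol*

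**What the plan says.** Protocol 16.3.1.2 fixes the origin of the Group 2 primary interval: "The interval will start 6 months after therapy start". It explains that at this point LR 6 is due to stop continuation therapy while LR 12 goes on for 6 more months. The next sentence is introduced as a consequence and gives the exclusion rule: "randomized patients with reactivations within the first 6 months after randomization will not be included in the analyses".

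Other places bear on the origin:

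- **16.1.2 (design):** "The randomization will be done in the local subcenter without delay after the first response evaluation 6 weeks after therapy start". Section 8.2.2 likewise makes response after 6 weeks of initial treatment a condition for randomisation.
- **9.2.1.3 (treatment):** continuation drugs run "until the end of month 6 or 12 from therapy start".
- **16.2.1.2 (primary aim):** the comparison is made "in those patients without disease reactivation within the first 6 months", with no origin stated.
- **16.5.2 (power):** "About 5% of these patients will show a reactivation within 24 weeks of treatment", which counts from the start of treatment.

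No section reconciles the two cut-offs in 16.3.1.2.

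**The concern.** The two cut-offs are presented as one but differ by the time from therapy start to randomisation, which is about 6 weeks. The protocol itself names month 6 from therapy start as the point where the arms separate, so those 6 weeks are the first in which the randomised treatments differ. A reactivation in that window is an event of the primary endpoint. Under the exclusion sentence it removes the patient from the analysis, whereas a patient without reactivation stays in with 6 weeks of guaranteed event-free time.

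This is selection on an outcome that the allocated treatment can affect, and it fits poorly with the intention-to-treat statement in 16.3. It is a separate matter from leaving out reactivations before month 6, when both arms are due the same treatment.

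The visit schedule makes it practical. Section 13 sets 6-weekly clinical examinations in the first year off therapy for patients without risk organ involvement. The first such visit in LR 6 falls at about week 32, on the exclusion boundary. Whether a reactivation found there is an event or a deletion could turn on a few days.

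At stake are who is in the primary analysis, which events count, and therefore when each event-timed look falls.

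**Working it through.** **Offset.** Six months is about 26 weeks, so the interval opens at about week 26 from therapy start. Randomisation is at about week 6, so the exclusion ends at about week 6 + 26 = 32. The window is 6 weeks, w = 6/52.18 = 0.115 year.

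**Inputs (16.5.2).** One-year reactivation free survival 65% (LR 6) and 85% (LR 12), exponential; loss to follow-up exponential with λ = 0.664 per year; 148 patients; about 6 years' recruitment; 2 years' minimum follow-up; 36 events. Assumed: 74 per arm, uniform entry, follow-up counted from the opening of the interval.

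**Hazards.** h = −ln(0.65) = 0.431 per year in LR 6 and −ln(0.85) = 0.163 in LR 12. Hazard ratio 0.163/0.431 = 0.377.

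**The plan's own event number.** Schoenfeld's formula, two-sided 5%, 80% power: 4(1.960 + 0.842)²/(ln 0.377)² = 33.0 events. Multiplying by the Group 1 group sequential inflation, 228/202 = 1.13, gives 37.3, rounded up to 38. The stated 36 is reproduced to within two events, so the inputs are read as the plan meant them.

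**Share of patients with an event in the window, 1 − exp(−h·w).**

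- LR 6: 4.8%
- LR 12: 1.9%

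**Expected events without the extra exclusion.** Per arm, 74 × h/(h + λ) × [1 − mean of exp(−(h + λ)u)], with u uniform from 2 to 8 years.

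- LR 6: 74 × 0.3935 × (1 − 0.0170) = 28.6
- LR 12: 74 × 0.1966 × (1 − 0.0383) = 14.0
- Total: 42.6

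**Events falling in the window.** Per arm, 74 × h/(h + λ) × [1 − exp(−(h + λ)w)].

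- LR 6: 74 × 0.3935 × 0.1183 = 3.44
- LR 12: 74 × 0.1966 × 0.0907 = 1.32
- Total: 4.76, or 11% of 42.6. About 37.9 remain.

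**Effect on the survival estimates.** Among those kept, nobody can have an event in the first 6 weeks, so each rate is divided by exp(−h·w): 0.9517 in LR 6 and 0.9815 in LR 12. Section 16.3.1.2 plans confidence intervals at 2 and 3 years.

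| Time | Without extra exclusion, LR 6 v LR 12 | Difference (points) | Literal rule, LR 6 v LR 12 | Difference (points) |
|---|---|---|---|---|
| 2 years | 42.3% v 72.3% | 30.0 | 44.4% v 73.6% | 29.2 |
| 3 years | 27.5% v 61.4% | 34.0 | 28.9% v 62.6% | 33.7 |

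Each curve sits 1 to 2 points too high. The difference shrinks by about 0.8 points at 2 years and 0.2 to 0.3 points at 3 years.

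**The case against.** The best reply is that this is a drafting slip. The exclusion sentence is offered as a consequence of opening the interval at 6 months from therapy start, and only reactivations before that date follow from it. Sections 9.2.1.3 and 16.5.2 both count from therapy start. That reading is probably right, and a reader should not infer that the plan deliberately chose to discard events after the arms separate. But the sentence is the operative rule for membership of a primary analysis, and an analyst who follows it gets a different population and event count.

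A reader might also infer that the test is biased or the trial underpowered. The documents do not support either.

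- **Validity.** Under the constant, proportional hazards that the plan assumes, removing the first 6 weeks leaves the hazard ratio at 0.377. If the arms are equal, equal expected fractions are removed from each, so no spurious difference arises. The small distortion of the difference runs against LR 12.
- **Power.** Section 16.4.2 times the looks by events and 16.5.2 requires 36. On the planned calendar about 37.9 events are still expected. In 6,000 simulated trials with a single non-sequential log-rank test, power went from 86.9% (42.6 events) to 82.5% (37.9 events), still above the 80% target. Taking the loss out of the 36, leaving about 32, would lower fixed-design power from 83% to 79%, but the plan does not provide for a final analysis at 32 events.
- **Clustering of reactivations just after stopping.** This would enlarge the loss, but nothing in the documents supports it and the plan assumes a constant hazard. It carries no weight here.

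**Conclusion.** The point holds: 16.3.1.2 gives two incompatible cut-offs for one primary analysis. If the exclusion is applied as written, primary events from the first 6 weeks of differing treatment are deleted on outcome: about 4.8 of 42.6 expected (11%), of which 3.4 are in LR 6 and 1.3 in LR 12. Both survival curves are then reported 1 to 2 points too high at the planned time points. The log-rank comparison stays valid under proportional hazards. If the final analysis waits for 36 events, the cost is mainly time: the expected margin over 36 falls from 6.6 to 1.9 events.

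These sizes rest on the plan's exponential hazards and loss rate, equal allocation, uniform entry, and randomisation at exactly week 6. Later randomisation would widen the window. The contradiction itself depends on none of these assumptions.

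**What to change.** In 16.3.1.2, change the time limit of the exclusion so that it covers reactivations *before 6 months after therapy start*, the date on which the interval opens. State the same origin in 16.2.1.2, where none is given. Add that every reactivation or death after that date counts as an event. Bringing the 24 weeks in 16.5.2 into line is optional: it already counts from therapy start and is about 2 weeks short of 6 months, within an approximate figure.

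The cost is a phrase in one section and a clarification in another, with no added patients, visits or data. Because the looks are timed by event count, the wording should be settled before an interim analysis relies on it.

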### **6.1.3 To assess acute and late treatment toxicity**

## **6.2 GROUP 2: MULTISYSTEM “LOW RISK” PATIENTS**

### **6.2.1 To decrease morbidity**

- by reducing the rate of reactivation and permanent consequences. The value of prolonged continuation therapy for responders to initial treatment and the efficacy of 6 versus 12 months continuation treatment will be tested in a randomized way.

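### Group 2 primary analysis: the clock starts 6 months after therapy start, but reactivations are excluded up to 6 months after randomisation, about 6 weeks after LR 6 has stopped

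*Protocol*

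**What the plan says.** - **Clock (16.3.1.2).** "The interval will start 6 months after therapy start, i.e. the time point when half of the patients are intended stop the continuation therapy" (arm LR 6), while LR 12 goes on for 6 more months. Reactivation and death are the events.
- **Exclusion (16.3.1.2, next sentence).** Presented as a consequence of that clock: "randomized patients with reactivations within the first 6 months after randomization will not be included in the analyses".
- **Randomisation (16.1.2).** "The randomization will be done in the local subcenter without delay after the first response evaluation 6 weeks after therapy start". Sections 8.2.2 and 10.3.2 agree.
- **Treatment duration (9.2.1.3).** Continuation runs "until the end of month 6 or 12 from therapy start", so LR 6 stops at month 6 from therapy start. Section 10.3.2 has the same stop.
- **Endpoint (16.2.1.2).** The comparison is made "in those patients without disease reactivation within the first 6 months", with no origin named.
- **Planning (16.5.2).** "About 5% of these patients will show a reactivation within 24 weeks of treatment", which counts from therapy start.
- **Analysis principle (16.3).** Under intention to treat, "the patients will be analyzed in their allocated treatment group, even in case of non-compliance or protocol violations".

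**The concern.** The clock and the exclusion have different origins, about 6 weeks apart. Up to month 6 both arms receive the same treatment, so leaving out earlier reactivations treats them alike, and a landmark there is defensible. After month 6 LR 6 is off treatment and LR 12 is on it. Dropping patients because they reactivate in that window selects on an outcome that the randomised difference can influence, and it falls mostly on LR 6.

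Four things are at stake:
- The primary comparison loses events.
- The patients who remain count as at risk for 6 weeks in which no reactivation can be recorded, so both Kaplan-Meier curves read too high.
- The event count that triggers the interim looks (16.4.2) depends on which of two adjacent sentences is followed.
- If the choice is left until data are in hand, it can be made with knowledge of its effect.

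**Working it through.** **1. Timeline from therapy start.** Six weeks is 42/30.4375 = 1.38 months, so 6 months after randomisation is 6 + 1.38 = 7.38 months.

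| Period | LR 6 | LR 12 | Clock | A reactivation is |
|---|---|---|---|---|
| Week 6 to month 6 | on therapy | on therapy | not started | excluded |
| Month 6 to 7.4 | off | on | running | an event and excluded |
| After month 7.4 | off | on to month 12 | running | an event |

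**2. The plan's own event number (16.5.2).** Yearly hazards are −ln 0.65 = 0.431 and −ln 0.85 = 0.163, so the hazard ratio is 0.163/0.431 = 0.377. The Schoenfeld formula, two-sided 5% with 80% power, gives 4 × (1.960 + 0.842)² / (ln 0.377)² = 33.0 events for a fixed design. The stated 36 implies a group-sequential inflation of 36/33.04 = 1.09, which is plausible beside 228/202 = 1.13 in Group 1. The 36 events are accepted.

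**3. Reactivations removed.** The window is 42/365.25 = 0.115 year. With exponential loss to follow-up of 0.664 per year (16.5.2), the chance of a reactivation in the window before loss is λ/(λ + 0.664) × [1 − exp(−(λ + 0.664) × 0.115)].
- LR 6: 0.431/1.095 × [1 − exp(−1.095 × 0.115)] = 4.65%; × 74 = 3.44.
- LR 12: 0.163/0.827 × [1 − exp(−0.827 × 0.115)] = 1.78%; × 74 = 1.32.
- Sum 4.76, with 3.44/1.32 = 2.6 times as many from LR 6.

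**4. Against the event totals.** With 148 patients, uniform accrual over 6 years and 2 years' minimum follow-up, the event probabilities are 38.7% and 18.9%, so 74 × (0.3868 + 0.1891) = 42.6 events are expected. After the exclusion 42.6 − 4.8 = 37.8 remain.
- Share of expected events: 4.76/42.6 = 11%.
- Relative to the 36 planned: 4.76/36 = 13%.
- Relative to one interim step of 36/5 = 7.2 events: 4.76/7.2 = 0.66.
- Patients needed to reach 36 events: 148 × 36/42.6 = 125 without the exclusion, 148 × 36/37.85 = 141 with it.

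**5. Kaplan-Meier rates with the clock at month 6.** Each curve is divided by its survival over the window, exp(−0.0495) for LR 6 and exp(−0.0187) for LR 12.

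| Time on clock | True rates | Difference | Rates as read | Difference |
|---|---|---|---|---|
| 1 year | 65.0% v 85.0% | 20.0 | 68.3% v 86.6% | 18.3 |
| 2 years | 42.3% v 72.3% | 30.0 | 44.4% v 73.6% | 29.2 |
| 3 years | 27.5% v 61.4% | 34.0 | 28.9% v 62.6% | 33.7 |

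**6. Power.** In 20,000 simulated trials (148 patients, the accrual and follow-up above, two-sided 5% log-rank, no interim looks) power was 86.6% with the month-6 landmark and 82.4% with exclusion to month 7.4.

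**7. Sensitivity (an assumption, not a protocol figure).** If the LR 6 hazard doubles to 0.862 in those 6 weeks, LR 6 loses 0.862/1.526 × [1 − exp(−1.526 × 0.115)] × 74 = 6.72. The total is then 6.72 + 1.32 = 8.04 events, 22% when set against 36.

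**The case against.** The strongest reply is that this is a slip of one phrase. The exclusion is introduced as following from the clock, and only exclusion up to month 6 from therapy start does follow from it. Sections 9.2.1.3, 10.3.2 and 16.5.2 all count from therapy start. That reading is probably what was meant. But the sentence as written is an explicit rule that a programmer could apply, and no section overrides it.

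Several points about size also stand:
- Even under the literal reading, the expected 37.8 events and 82–83% power stay above the planned 36 and 80%, although that power ignores the interim looks. Because looks are triggered by events, lost events mainly delay them.
- The events come out of the 42.6 expected, so 11% is the fairer share; 13% sets them against the planned number.
- Section 16.3.1.2 asks for confidence intervals at 2 and 3 years, where the difference shrinks by only 0.8 and 0.2 points. The 1.7-point loss is at 1 year, the planning time point.
- The log-rank test is the primary test, and 16.3.1.2 expects proportional, constant hazards. Under them the hazard ratio is not biased. Nothing in the protocol shows clustering after LR 6 stops.
- The intention-to-treat sentence in 16.3 concerns analysis by allocated arm, and any month-6 landmark also drops randomised patients. The objection is therefore specific to exclusions made after the arms diverge.

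In addition, the exclusion names reactivations only. Deaths in the window would still count, though section 2 reports none among low-risk patients in LCH II.

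**Conclusion.** The concern holds. Section 16.3.1.2 defines the primary analysis set with two incompatible origins, and the literal rule removes patients on outcome during the first 6 weeks in which the arms differ. At the planning rates the cost is about 4.8 of 42.6 expected events, about 4 points of power and a 1.7-point smaller difference at 1 year. The effect at 2 and 3 years is small, and the hazard ratio is unbiased if hazards are constant. These figures assume that the planning hazards apply from month 6, 74 patients per arm, uniform accrual and randomisation exactly at week 6. Clustering of LR 6 reactivations after stopping would enlarge the loss and pull the hazard ratio towards 1. This does not invalidate the trial, but it should be corrected before the first interim look.

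**What to change.** In 16.3.1.2, change the exclusion so that the 6 months run from therapy start instead of from randomisation. Clock, exclusion and the LR 6 stop in 9.2.1.3 and 10.3.2 then share one landmark, the gap is zero and the 36-event plan stands. Naming the same origin in 16.2.1.2 would help the reader but is optional. The 24-week planning figure in 16.5.2 and the references to 6 versus 12 months of continuation (such as 6.2.1) can stay, because 9.2.1.3 fixes the arms from therapy start.

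The cost is a wording change, with no extra patients, visits or data.
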